## 9.4.2. Erythropoiesis-Stimulating Agent Usage

If a patient experiences chemotherapy-induced anemia (hemoglobin level <10 g/dL) after receiving the first dose of study treatment, ESAs may be used per ASCO guidelines and the current prescribing information (Bohlius, 2019) (Procrit®, 2017; Aranesp®, 2011).

G1T28-213

#### 9.4.3. Transfusions

#### Red Blood Cells

Based on the NCCN Clinical Practice Guidelines in Oncology for Hematopoietic Growth Factors Version 2.2020 and the AABB Clinical Practice Guidelines, the following RBC transfusion thresholds are recommended (Carson, 2016; Goel, 2018); however, the patient's clinical situation should always be the primary guiding factor when deciding to transfuse.

- Transfusion is not indicated until the hemoglobin level is ≤7 g/dL for hospitalized adult patients who are hemodynamically stable.
- An RBC transfusion threshold of ≤8 g/dL is recommended for patients undergoing orthopedic surgery, cardiac surgery, and those with preexisting cardiovascular disease.
- Patients with symptomatic anemia should be transfused per the Investigator discretion regardless of hemoglobin levels.

## **Platelets**

Platelet transfusion is recommended at a threshold of  $\leq 10 \times 10^9/L$ . Platelets should also be transfused in any patient who is bleeding with a platelet count  $\leq 50 \times 10^9/L$  (100 x 10^9/L for central nervous system or ocular bleeding) (Kaufman, 2015; Schiffer, 2001).

## 9.5. Prior/Concomitant Medications and Procedures

All prior and concomitant medications including prescription medications, over-the-counter preparations, supplements, herbal remedies, growth factors, and blood products from informed consent through 30 days after the last dose of study treatment (Safety Follow-up Visit) will be documented, where possible.

Avoid concomitant use of trilaciclib with certain OCT2, MATE1, and MATE-2K substrates (e.g., dofetilide, dalfampridine) where minimal concentration changes may lead to serious or life-threatening toxicities. Refer to the prescribing information for these concomitant medications for assessing the benefit and risk of concomitant use of trilaciclib.

**Avoid administering UGT1A1 inhibitors with sacituzumab govitecan-hziy**. Concomitant administration of sacituzumab govitecan-hziy with inhibitors of UGT1A1 may increase the incidence of adverse reactions due to potential increase in systemic exposure to SN-38.

**Avoid administering UGT1A1 inducers with sacituzumab govitecan-hziy.** Exposure to SN-38 may be substantially reduced in patients concomitantly receiving UGT1A1 enzyme inducers.

Administration of other concomitant investigational agents for any indication or any live attenuated vaccines is not permitted while on this study. Necessary supportive care (antiemetics, antidiarrheals, chemotherapy premedication, etc.) per the standard of care at the study center will be permitted. See Section 9.4 for guidance on the use of growth factors (colony-stimulating factors and ESAs) during the study.

Administration of other systemic concomitant non-protocol anticancer therapies prior to progression is not permitted while on this study. Palliative treatment of a symptomatic

G1T28-213

lesion(s) is permitted to control disease symptoms but not to aid in the response of the tumor. If the lesion(s) treated is being followed for evaluation by RECIST v1.1 (target or nontarget lesion), then "not evaluable" should be reported in EDC for this lesion at subsequent disease assessments following palliative treatment. Patients requiring palliative therapy may continue receiving study drug until documented disease progression (radiographic or clinical) if, in the Investigator's opinion, the patient is continuing to receive clinical benefit and they meet the requirements described in Section 9.2. However, for patients who have not had disease progression at the time of the need for palliative radiation therapy or surgery, the requirement for intervention will be regarded as disease progression in the study's analyses and will be entered as such in the EDC.

Any diagnostic, therapeutic, or surgical procedures performed during the study period will be documented. Documentation will include information regarding the date(s), indication(s), description of the procedure(s), and any clinical or pathological findings, if available.

## 9.6. Measures to Minimize Bias

The study will be single-arm and open-label.

Patients that are enrolled, received at least one dose of study drug, and discontinue from the study will not be replaced. Patients that are enrolled but did not receive any study drug may be replaced upon approval of the Medical Monitor and Sponsor.

# 9.7. Intervention after End of Study Treatment

Following completion of study treatment on the study, patients will receive treatment as determined by their healthcare provider. During Survival Follow-up, the patient (or legally authorized representative where allowed by local regulation) will be contacted to record their status (alive or dead) as well as details of any subsequent systemic anti-cancer therapy initiated (see Section 11.7).

G1T28-213

# 10. DISCONTINUATION OF STUDY INTERVENTION AND PATIENT DISCONTINUATION/WITHDRAWAL

# 10.1. Discontinuation of Study Treatment

Study drugs will be discontinued if any of the following events occur during the study:

- A patient suffers an AE that, in the judgment of the Investigator, Sponsor, or Medical Monitor, presents an unacceptable risk to the patient
- General or specific changes in the patient's condition (e.g., a significant intercurrent illness or complication) that, in the judgment of the Investigator, are unacceptable for further administration of study drug
- Occurrence of pregnancy in a female patient during the study
- Significant noncompliance with protocol requirements
- The Sponsor or legal representative of the Sponsor requests the patient to withdraw
- Patient has documented disease progression (radiographic or clinical progression).
   See Section 9.5 for details regarding palliative therapy.
- If the total time from a scheduled sacituzumab govitecan-hziy dose exceeds a total of >3 weeks, unless agreed to by the treating Investigator and Medical Monitor.
- Where permanent discontinuation of any study drug is indicated in the toxicity management recommendations (Section 9.3).

At the time of study drug discontinuation, an End of Treatment Visit should be completed with assessments performed as shown in the Schedule of Assessments (Table 6). The Investigator or Designee will document the reason for study drug discontinuation on the applicable eCRF. When discontinuation is due to a SAE or a Grade 3 or 4 toxicity considered to be related to study drug, the Investigator should follow the event until resolution, return to baseline, or it is deemed that further recovery is unlikely. Data on these events should be collected on the AE eCRF. In the event a patient discontinues due to pregnancy, the Investigator or designee should notify the Medical Monitor by telephone within 24 hours of pregnancy confirmation (see Section 17.3).

For those patients who have not progressed clinically or radiologically at the time of study drug discontinuation, every effort should be made to continue radiological tumor assessments every 12 weeks ( $\pm 7$  days) during survival follow-up, utilizing the same imaging modality as used at Screening as outlined in the Schedule of Assessments (Table 6), until progressive disease, initiation of subsequent anti-cancer therapy, withdrawal of consent, or study completion, whichever occurs first. Results of these scans should be assessed by RECIST v1.1 and data entered in EDC in the corresponding tumor assessment forms.

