# 12.1. Sample Size Determination

The sample size is calculated to support the primary objective of the study, that is, to evaluate trilaciclib's effect on PFS when administered prior to sacituzumab govitecan-hziy in patients with locally advanced or metastatic TNBC who received at least 2 prior treatments with at least 1 in the metastatic setting.

This single-arm study plans to enroll 45 patients during the 10-month accrual period with an approximate 30-month total study duration. With 45 patients and 14 months of follow-up after the last patient is dosed, Table 12 presents the required number of PFS events and statistical powers to detect HRs of 0.7 and 0. 8 at a 2-sided significance of 0.2 for a median PFS of the historical control group of 5.6 months, which was defined for patients without brain metastases treated with sacituzumab govitecan-hziy in the Phase 3 ASCENT trial (Bardia, 2021). The calculation is based on one-sample log-rank test (Wu, 2015) with the assumption that the survival time distributions for both study treatment and historic control group follow the Weibull distribution with a shape parameter of 1.00 (i.e., exponential distribution).

**Table 12:** Statistical Power

Hazard Ratio	Median PFS for trilaciclib + sacituzumab govitecan-hziy (Months)	•	Statistical Power
0.70	8.0	36	80%
0.80	7.0	38	54%

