# 17.4. Definitions of Tumor Response and Disease Progression (per RECIST v1.1)

The determination of tumor response and progression will be based on the RECIST v1.1 (Eisenhauer, 2009). Disease progression may also be determined clinically by the Investigator. Tumor lesions will be categorized as follows:

**Measurable lesions**: tumor lesions with a longest diameter (measured in at least 1 dimension) with a minimum size as follows:

- 10 mm by CT or MRI (with a scan slice thickness of no greater than 5 mm)
- Measurable lymph nodes must be ≥15 mm on the short axis by CT or MRI (with a scan slice thickness of no greater than 5 mm); only the short axis is to be measured at baseline and follow-up.
- Bone lesions: Bone scan, PET scan, or plain films are not considered adequate
  imaging techniques to measure bone lesions. However, these techniques can be used
  to confirm the presence or disappearance of bone lesions. Lytic bone lesions or mixed
  lytic-blastic lesions, with identifiable soft tissue components, that can be evaluated by
  cross-sectional imaging techniques such as CT or MRI can be considered measurable
  lesions if the soft tissue component meets the definition of measurability described
  above. Blastic bone lesions are non-measurable.
- Cystic lesions representing cystic metastases that meet the definition of measurability described above can be considered measurable lesions. If present, noncystic lesions should be selected as target lesions for this study.
- A tumor lesion that has been previously irradiated may be considered measurable if unequivocal growth of the lesion has been demonstrated.

**Target lesions**: At baseline, up to 5 measurable tumor lesions/lymph nodes (with a maximum of 2 lesions per organ) should be identified as target lesions. Lesions with the longest diameter, that are representative of all involved organs, and for which reproducible repeated measurements can be obtained should be selected as the target lesions. Malignant lymph node is considered an organ in this study, therefore only 2 malignant lymph nodes (regardless of location) may be selected as target lesions and all others should be entered as nontarget lesions.

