#### **Timepoint Response**

#### Patients with Measurable Disease (i.e., Target ± Non-Target Disease)

Target	Non-Target Lesions	New Lesions	Overall Response
Lesions			
CR	CR	No	CR
CR	Non-CR/Non-PD	No	PR
CR	NE	No	PR
PR	Non-CR/Non-PD/NE	No	PR
SD	Non-CR/Non-PD/NE	No	SD
NE	Non-PD	No	NE
PD	Any	Yes or No	PD
Any	$\mathrm{PD}^{\mathrm{a}}$	Yes or No	PD
Any	Any	Yes	PD

CR=complete response; NE=not evaluable; PD: progressive disease; PR=partial response; SD=stable disease.

G1T28-213

Note: Patients with a global deterioration of health status requiring discontinuation of treatment without objective evidence of disease progression at that time should be reported as "*symptomatic deterioration*." Every effort should be made to document the objective progression even after discontinuation of treatment.

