1.3. Sample Size Consideration

The initial sample size was calculated to support the primary objective of the study, that is, to evaluate trilaciclib's effect on PFS when administered prior to sacituzumab govitecan-hziy in patients with locally advanced or metastatic TNBC who received at least 2 prior treatments with at least 1 in the metastatic setting.

This single-arm study was initially planned to enroll 45 patients during the 10-month accrual period with an approximate 30-month total study duration. With 45 patients and 14 months of follow-up after the last patient is dosed, Table 2 presents the required number of PFS events and statistical powers to detect hazard ratios (HRs) of 0.7 and 0. 8 at a 2-sided significance of 0.2 for a median PFS of the historical control group of 5.6 months, which was defined for patients without brain metastases treated with sacituzumab govitecan-hziy in the Phase 3 ASCENT trial (Bardia, 2021). The calculation is based on a one-sample log-rank test (Wu, 2015) with the

assumption that the survival time distributions for both study treatment and historic control group follow the Weibull distribution with a shape parameter of 1.00 (i.e., exponential distribution). PASS 2019, v19.0.8 was used for the power and sample size calculation.

Table 2Statistical Power

Hazard Ratio	Median PFS for trilaciclib + sacituzumab govitecan-hziy (Months)	Expected number of events in the study	Statistical Power
0.70	8.0	36	80%
0.80	7.0	38	54%

On February 14, 2023, the sponsor decided to close enrollment to this study in order to reallocate resources to other ongoing trilaciclib clinical trials. The final sample size is 30.

G1 Therapeutics

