3.2. The Response Evaluable Population

The Response Evaluable (RE) population includes all patients who are in the FAS, have measurable (target) tumor lesion(s) at baseline tumor assessment per RECIST v1.1, and have either of the following:

- 1. At least one post-baseline tumor assessment.
- 2. Discontinued treatment because of clinical progression prior to the first post-baseline tumor scan.
- 3. Died due to disease progression prior to the first post-baseline tumor scan.

The RE population will be the primary population for efficacy endpoints evaluating tumor responses.

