8.1. Definitions of Efficacy Endpoints

8.1.1. Primary Efficacy Endpoints – Progression Free Survival

Progressive disease (PD) and tumor response status are programmatically determined according to RECIST v1.1 based on the radiographic tumor assessment data recorded on the eCRF by the Investigator for target lesions, the investigator assessment of non-target lesions, and the status of new lesions. For a patient, the status of PD will be determined using all radiographic tumor scan data assessed prior to or on the date of the data cutoff to conduct the analysis for PFS. In the situation where PD and withdrawal of consent or PD and initiation of subsequent anticancer therapy occurred on the same day for a patient, the PD status will be assumed for that patient.

Radiographic PD and death due to any cause during the study are referred to as PFS events.

PFS is defined as the time (months) from date of C1D1 to the date of the first documented disease progression, or death in the absence of PD for those who had a PFS event, and the time from date of C1D1 to the censoring date for those who did not have a PFS event. Specifically, PFS is calculated as (date of PFS event or censoring – date of C1D1+ 1)/ 30.4375. The analysis for PFS will be based on the FAS.

Details for PFS calculation and censoring rules can be found in Table 6.

Situation	Date of Event or Censoring	Outcome
Disease progression per RECIST Version 1.1	Date of the first documented progression	PFS event
Death without a PD	Date of death	PFS event
Incomplete or no baseline tumor assessments	Date of C1D1	Censored
No progression	Date of the last adequate radiological tumor assessment with no documented disease progression	Censored
Treatment discontinuation for reasons other than disease progression	Date of the last adequate radiological tumor assessment with no documented progression	Censored
Subsequent anticancer treatment started prior to documented disease progression	Date of last adequate radiologic assessment prior to or the date of initiation of subsequent anticancer treatment	Censored

Table 6PFS Calculation and Censoring Rules

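### Patients who stop drug for clinical progression fall outside the continued-scan request and have no rule of their own for PFS, which lengthens median PFS relative to a PFS that counts clinical progression

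*Protocol*

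**What the plan says.** **Stopping drug.** Protocol 10.1 discontinues study drug on documented progression, whether radiographic or clinical. Protocol 17.4 adds: "Disease progression may also be determined clinically by the Investigator".

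**Scanning after stopping.** Protocol 10.1 requests continued 12-weekly assessments "For those patients who have not progressed clinically or radiologically at the time of study drug discontinuation", and 11.2.1 repeats the condition. The Note under the timepoint-response table in 17.4 concerns patients who stop because their health deteriorates without objective evidence of progression. It says: "Every effort should be made to document the objective progression even after discontinuation of treatment".

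**What counts.** SAP 8.1.1: "Radiographic PD and death due to any cause during the study are referred to as PFS events". SAP Table 6 has rows for radiographic progression, death without progression, missing baseline, no progression, discontinuation for reasons other than progression, and new anticancer therapy before progression. It has none for clinical progression. SAP 8.2.2 plans Kaplan-Meier estimates and no sensitivity analysis of PFS.

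**Elsewhere.** SAP 3.2 admits a patient to the response-evaluable population who "Discontinued treatment because of clinical progression prior to the first post-baseline tumor scan". Protocol 9.5 says that a need for palliative radiation or surgery before progression will be treated as progression in the analyses. Table 6 does not carry that rule.

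**The concern.** Patients whom the investigator judges to be progressing are the ones for whom further scans are not requested under 10.1 and 11.2.1. If no scan documents progression before new therapy starts, they leave the PFS risk set as censored observations at a scan that predates the deterioration. That censoring is informative. If they die without new therapy they do count, but at death and not when the disease was judged to have progressed.

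The two analysis sets also treat the same patient differently. A patient with clinical progression before the first post-baseline scan stays in the response denominator and cannot be a responder. If alive and without radiographic progression, that patient contributes no failure to the primary endpoint. The trial has no control arm to absorb a shift in the estimate, and with 30 patients a handful of such cases can move the median.

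**Working it through.** **1. The plan's own figures.** Inputs are from Protocol 12.1: "This single-arm study plans to enroll 45 patients during the 10-month accrual period"; "With 45 patients and 14 months of follow-up after the last patient is dosed"; control median 5.6 months; exponential PFS; two-sided alpha 0.2 (one tail 0.10, z = 1.2816).

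Expected events = N × [1 − (e^(−14λ) − e^(−24λ)) / (10λ)], with λ = HR × ln 2 / 5.6.

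- HR 0.70: λ = 0.0866; 45 × [1 − (0.2973 − 0.1250)/0.866] = 36.05 events.
- HR 0.80: λ = 0.0990; 45 × [1 − (0.2500 − 0.0929)/0.990] = 37.86 events.

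Power ≈ Φ(√d × |ln HR| − 1.2816):

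- d = 36, HR 0.70: Φ(2.140 − 1.282) = 80.5%.
- d = 38, HR 0.80: Φ(1.376 − 1.282) = 53.7%.

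The one-sample log-rank formula with the expected-events variance gives 79.5% and 53.6%. The stated 36 events with 80% and 38 events with 54% reproduce, so the sample-size arithmetic is sound. The final number enrolled is lower (SAP 1.3: "The final sample size is 30").

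**2. Following one patient through the rules.** The patient stops drug for clinical progression with no radiographic progression on file.

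- Scan later shows progression before new therapy: event at that scan.
- Alive, no such scan, with or without new therapy: censored at the last adequate scan (no-progression or new-therapy row).
- Dies without new therapy: event at death.
- Starts new therapy, then dies without documented progression: Protocol 12.4.6.1 says such a death is always an event. In SAP Table 6 both the death row (event) and the new-therapy row (censored) fit, and no precedence is given.

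**3. Size, under stated assumptions.** The documents give no rate of clinical-only progression, so a share q is assumed. True time to any progression is exponential with median 5.6 months. Scans follow the protocol schedule (6-weekly to Week 36, then 9-weekly), with 10 months' accrual and 14 months' follow-up. Clinical-only progressors are either censored at the previous scan or counted at a later death. Kaplan-Meier medians in months, from large simulated samples:

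| Share q | All censored | Half count at death (median 3 months later) | All count at death (median 2 months later) |
|---|---|---|---|
| 0 | 5.6 | 5.6 | 5.6 |
| 10% | 6.2 | 6.1 | 5.9 |
| 20% | 6.9 | 6.7 | 6.3 |
| 30% | 7.8 | 7.3 | 6.6 |

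If all count at death but with a median 6 months later, the results are close to the all-censored column (6.2, 6.9, 7.7). As a check, the all-censored case is near 5.6/(1 − q): 5.6/0.9 = 6.2, 5.6/0.8 = 7.0, 5.6/0.7 = 8.0. Counting clinical progression as an event when it occurs returns 5.6 months.

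**4. Illustration on the design's test.** With N = 30 and no drug effect, the chance of passing a one-sided 0.10 one-sample log-rank test rises from about 0.10 to 0.14-0.25 at q = 10% and 0.18-0.41 at q = 20%. The SAP plans no such test, so this shows sensitivity only and is not an error rate of the trial.

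**The case against.** The case on the other side is substantial.

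- **Scanning is not stopped.** A reader might infer that no radiographic progression can be recorded for these patients. The documents do not support that. Sections 10.1 and 11.2.1 only leave these patients out of a request, 11.2.1 allows extra scans when clinically indicated, and the 17.4 Note covers this very patient. SAP 8.1.1 uses all scans up to the cutoff. What stands is a contradiction between passages. Footnote b of the schedule of assessments does not resolve it: it scans until documented progression, a term that Protocol 9.5 and 10.1 use for clinical progression too.
- **Not all are censored.** Death without progression is an event, and PFS is now analysed at about 21 deaths among 30 patients. This reduces the shift but does not remove it: the all-count-at-death column still exceeds 5.6 months.
- **The comparison with 5.6 months.** A reader might infer that the result is biased upward against the benchmark, or that 20-30% clinical-only progression would reproduce the planned medians of 7.0 and 8.0 months with no drug effect. Neither is supported. The historical trial's rule is not given, and if it was also radiographic-only the handling may match. The benchmark enters as a sample-size input, with no decision rule attached. The values 7.0 and 8.0 come from the closed-form all-censored extreme at assumed rates.
- **Radiographic-only PFS is a deliberate choice.** Counting investigator judgement in an open-label trial adds subjectivity. That is a good reason to leave the primary definition alone, but it does not argue against a labelled sensitivity analysis.
- **Some reporting exists.** SAP 8.2.2 tabulates censoring reasons and SAP 5.1 discontinuation reasons. Table 6 nevertheless gives clinical progression no category of its own.

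**Conclusion.** The point holds in limited form. The scan request in Protocol 10.1 and 11.2.1 conflicts with the 17.4 Note, and the SAP has no explicit PFS rule for clinical progression. As written, the plan can produce informative censoring or late-counted events, and both lengthen median PFS relative to a PFS that counts clinical progression. The direction was the same in every scenario tried.

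The ranges of 5.9-6.2, 6.3-6.9 and 6.6-7.8 months at 10%, 20% and 30% rest on assumed clinical-only rates, assumed death times and a constant hazard. The true rate may be lower, and later scans that document progression would shrink the shift. Whether the estimate is biased against the historical 5.6 months cannot be settled from these documents. The contrast with the response analysis is confined to clinical progression before the first post-baseline scan; later cases enter through their scans and may be responders.

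**What to change.** 1. **Protocol 10.1, 11.2.1 and 17.4:** reconcile the passages so that objective progression is sought in patients who stop for clinical progression until radiographic progression, new anticancer therapy or withdrawal.
2. **SAP 8.1.1 and Table 6:** keep the radiographic primary definition. Add clinical progression as a named censoring reason, and state which row governs a death after new therapy.
3. **SAP 8.2.2:** report the number of patients censored after clinical progression. Add one sensitivity Kaplan-Meier analysis on the full analysis set that counts discontinuation for clinical progression, without prior radiographic progression, as an event. Date it at the recorded clinical-progression date or, failing that, at study drug discontinuation. State how the palliative-intervention rule of Protocol 9.5 is handled.
4. **Labelling:** present it as sensitivity only, since it includes investigator judgement and may not match the definition behind the 5.6-month benchmark. It is pre-specified only if added before database lock; after lock, report it as post hoc with the rationale in the study report.

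**Cost.** The SAP part is a few lines and one extra analysis. The discontinuation reason is on the eCRF (Protocol 10.1), and SAP 6.3 already uses the date of study drug discontinuation. The protocol part is an amendment needing ethics approval (Protocol 13.1) and cannot recover scans already missed. With enrollment closed at 30, the SAP change matters more. The likely downside is a slightly less favourable sensitivity median.
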